7 DATA ANALYSIS AND STATISTICAL CONSIDERATIONS

This is a phase 2, single center, basket study of oral BXCL701 daily on days 1-14 in combination with intravenous PD1/PDL1 antibody on day1 of 21-day cycle in subjects with advanced and refractory malignancies. Lead-in cohort will enroll 6 patients. Only the 6 patients treated at the selected dose during safety lead-in will be assigned to Cohort A or B as appropriate. That is, if there is a dose de-escalation during safety lead-in, then the 6 patients treated at the higher dose will not be assigned to the phase II cohorts. Cohorts A and B will enroll 9 to 17 patients. Response assessments with CT and/or MRI will be done every 9 weeks (3 cycles) following RECIST and iRECIST criteria.[19, 20] Intervals can be shortened to 6 weeks (2 cycles) if clinically necessary per treating physician.

The study will follow the BOP2 design with the following operating characteristics.

Power: 0.80

Type I error: 0.05

P0:0.05**P1:**0.25

Each cohort will enroll 9 patients. If there is no complete (CR) or partial response (PR) in the first 9 patients the enrolment to that cohort will stop. If there ≥ 1 PR or CR in the first 9 patients the enrollment will continue to enroll total of 17 patients. PR or CR does not require confirmation. The treatment will be considered promising for further exploration if ≥ 3 CRs or PRs are observed in 17 patients. The expected **Sample Size** will range from 9 (if terminated after safety lead in) to 34 patients. Accounted for ~20% of patients not being evaluable for efficacy, the actual number of patients to be recruited for the trial will range from 11 to 42.

Scenarios (PA, PB)	Pr(reject H0 for cohort A)	Pr(reject H0 for cohort B)	Average sample size for cohort A	Average sample size for cohort B
(0.05,0.05)	0.046	0.046	12.0	12.0
(0.05,0.25)	0.046	0.813	12.0	16.4
(0.25,0.25)	0.813	0.813	16.4	16.4
(0.05,0.15)	0.046	0.455	12.0	15.1
(0.15,0.15)	0.455	0.455	15.1	15.1
(0.15,0.25)	0.455	0.813	15.1	16.4

Operating characteristics:

Note: PA is the response rate for cohort A, PB is the response rate for cohort B.

The Investigator is responsible for completing toxicity/efficacy summary reports and submitting them to the IND office Medical Affairs and Safety Group for review. These should be submitted as follows:

• Lead-In Stage:

After the first 6 evaluable patients, complete cycle 1 of study treatment. IND Office approval must be obtained prior to advancing to the efficacy stage.

• Efficacy Stage:

After the first 9 evaluable patients per cohort, complete 9 weeks of study treatment, and after a total of 17 patients per cohort have completed 9 weeks of study treatment. A copy of the cohort summary should be placed in the Investigator's Regulatory Binder under "sponsor correspondence".

Toxicity monitoring is also performed in this stage. If the empirical DLT rate > 33%, we will suspend accrual for safety and discussions for the next step will be made.

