3 STUDY DESIGN

This is an open-label, single-institution, Phase 2 study to determine the response rate of BXCL701 administered orally and daily, combined with pembrolizumab, in patients with

advanced solid cancers. The study will also assess other efficacy parameters, such as PFS, OS and DOR, as well as the safety the combined treatment. Bayesian optimal phase 2 (BOP2) design will be adopted to monitor efficacy. The study will consist of 2 stages:

[figure not shown]
- Lead-in Stage (first 6 patients enrolled) in which the safety and tolerability of the combination of BXCL701 administered orally twice a day on Days 1 to 14 of a 21day cycle plus pembrolizumab 200 mg administered intravenously (IV) on Day 1 every 21 days will be assessed and confirmed in patients with advanced solid cancers. The dose of BXCL701 will be 0.6 mg divided in two doses (0.3 mg twice a day).
- 2) Efficacy Stage (BOP2-Stage) in which patients with advanced solid cancers will be treated with BXCL701 combined with pembrolizumab. Patients enrolled to the Lead-in Stage will be also evaluated in the efficacy stage. Starting from Protocol version 7, new patients enrolled will be administered BXCL701 at the starting dose of 0.2 mg orally twice a day for the first 7 days. If well tolerated and in the absence of signs and symptoms of clinically significant hypotension the dose will be escalated to 0.3 mg orally twice a day.

During the Lead-in Stage, patients will be observed for dose-limiting toxicity (DLT) during Cycle 1. Six patients will be treated initially with 0.3 mg BXCL701 twice a day (Days 1 to 14) plus pembrolizumab 200mg:

- If > 1 of the 6 original patients has a DLT in Cycle 1, the dose will be considered above the maximum tolerated dose (MTD) and additional 6 patients will be treated at the 0.4 mg BXCL701 daily Days 1 to 14 dose level.
 - If ≤ 1 of the patients experience a DLT, the Efficacy Stage can commence
 - \circ If > 1 of the patients experience a DLT, a discussion will be held between the investigators and supporters as to how to proceed

The study schema is presented in Figure 1.

DLT = dose-limiting toxicity; pembro = pembrolizumab; PR, partial response; CR, complete response

All safety data from all patients, who received at least one dose of study drug will be included in safety analysis. Unless doses were held because of DLT, a patient must have

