received >70% of their BXCL701 in Cycle 1 (i.e., \geq 30 of 42 planned doses) with pembrolizumab dosed on Day 1 of Cycle 1 to be eligible for DLT assessment.

Toxicities will be assessed by the investigator using the National Cancer Institute Common Terminology Criteria for Adverse Events (NCI CTCAE), version 5. The relationship of an AE to combination therapy (i.e., attribution to BXCL701 and/or pembrolizumab) is to be assessed by the investigator using the criteria in the protocol (Section 5.3.1).

A DLT is defined as any of the following AEs occurring during Cycle 1, regardless of investigator attribution to study treatment, unless the AE can be clearly and incontrovertibly attributed to an extraneous cause (e.g., disease progression) by the Principal Investigator:

- Any Grade 4 laboratory abnormality, regardless of duration.
- Any Grade 3 laboratory abnormalities if associated with clinical symptoms regardless of duration
- Any Grade ≥3 non-hematologic AE, with the exceptions of Grade ≥3 nausea, vomiting, diarrhea, constipation, and fatigue, that resolves to Grade ≤1 within 72 hours with optimal medical management and/or supportive measures.
- Grade ≥3 thrombocytopenia with Grade >1 bleeding or requirement for platelet transfusion.
- Grade \geq 3 febrile neutropenia.
- Grade ≥ 3 fever.
- Grade ≥ 3 skin rash.
- Laboratory abnormalities meeting Hy's law criteria (aspartate aminotransferase [AST] or alanine aminotransferase [ALT] >3 × upper limit of normal [ULN] with concomitant total bilirubin >2 × ULN).
- Any toxicity resulting in \geq 30% held/skipped doses of BXCL701 during Cycle 1.
- Delay of Cycle 2 by ≥ 14 days due to toxicity.
- Any other significant toxicity considered by the investigator and supporter's medical representatives to be dose-limiting.

Efficacy Stage:

After assessment of the safety and confirmation of the BXCL701/pembrolizumab2 dose schedule to be used in the subsequent stage, the Efficacy Stage will begin. Eligible patients will receive oral BXCL701 daily on Days 1 to 14 of a 21-day cycle plus pembrolizumab 200 mg administered IV on Day 1 every 21 days.

Study Design Features (Both Stages):

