proposed to be 0.6 mg daily, i.e., the previously identified recommended Phase 2 dose. The dose will be divided into two doses (0.3 mg twice a day) to minimize the risk of hypotension. Based on a review of emerging data from the BXCL701 program, the dosing schedule in the Efficacy Stage will be modified to implement a step-up dosing schedule during Cycle 1. The intent of step-up dosing is to immediately address a potentially serious side effect of hypotension that appears most likely to occur during the first week of treatment in Cycle 1. BioXcel has evaluated BXCL701 0.4 mg total daily dose with pembrolizumab during Phase 1b of the prostate cancer study and it was well-tolerated, with no DLTs experienced. In the Phase 1b cohort, none of the three patients experienced adverse events consistent with cytokine activation considered related to BXCL701. Therefore, the Bioxcel program is incorporating a one-week lead-in dosing period of 0.2 mg BID to potentially mitigate the effects of cytokine activation, including hypotensive events, which seem to predominantly occur during the first week of treatment in patients starting with 0.3mg BID. Escalation to 0.3 mg BID in patients demonstrating tolerance after one week of treatment is important since it is the dose that was previously associated with objective responses during prior development of BXCL701. Therefore, starting from Protocol version 7, new patients enrolled will be administered BXCL701 at the starting dose of 0.2 mg orally twice a day for the first 7 days. If well tolerated and in the absence of signs and symptoms of clinically significant hypotension the dose will be escalated to 0.3 mg orally twice a day.

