6.5 Pembrolizumab Administration, Dose Modifications and Discontinuation

Pembrolizumab will be prepared, stored, and administered according to the current full Prescribing Information. Pembrolizumab will be obtained from commercial supplies and will be administered 200 mg intravenously over 30 minutes through a 0.2 to 5 micron sterile, nonpyrogenic, low-protein binding online or add-on filter. No other medication will be infused through the infusion line. Infusion will be interrupted and slowed for grade 1 or 2 infusion-related reactions and permanently discontinued for grade 3 or 4 infusion-related reactions. Pembrolizumab will be administered until disease progression, unacceptable toxicity, or withdrawal of consent.

AEs associated with pembrolizumab exposure may be immune-mediated. Immune-related AEs may occur any time after pembrolizumab administration and may affect multiple body systems. Early recognition and treatment are important to reduce complications. Most immune-related AEs are reversible and can be managed with discontinuation of pembrolizumab and initiation of steroids. Refer to the current regional pembrolizumab full Prescribing Information for recommended dose modifications for the management of toxicities (including immune-mediated reactions and infusion-related reactions) considered related to pembrolizumab. Patients who require a dose hold of pembrolizumab of \geq 42 days will be discontinued from the study.

Pembrolizumab should not be used in conjunction with other immunosuppressive agents other than corticosteroids administered for control of immune reactions considered related to pembrolizumab. Refer to the current regional pembrolizumab full Prescribing Information for further details.

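### No prespecified accrual criterion in the Efficacy Stage covers toxicity that first occurs after Cycle 1

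*Combined protocol and SAP*

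**What the plan says.** Section 7, on toxicity monitoring in the Efficacy Stage: "If the empirical DLT rate > 33%, we will suspend accrual for safety and discussions for the next step will be made". It gives no separate Efficacy Stage definition of a DLT.

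The only definition is in Section 3: "A DLT is defined as any of the following AEs occurring during Cycle 1, regardless of investigator attribution to study treatment", with an exception for clearly extraneous causes. The lead-in text uses the same window: "During the Lead-in Stage, patients will be observed for dose-limiting toxicity (DLT) during Cycle 1". Two items on the list might seem to reach further. One is "Delay of Cycle 2 by ≥ 14 days due to toxicity"; the other is the catch-all item, "Any other significant toxicity considered by the investigator and supporter's medical representatives to be dose-limiting". Both sit under the Cycle 1 stem, and the first concerns only the start of Cycle 2.

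Section 6.5 continues pembrolizumab until progression, unacceptable toxicity or withdrawal of consent, and says: "Immune-related AEs may occur any time after pembrolizumab administration and may affect multiple body systems". Section 3.1 introduces a step-up with version 7 of the protocol: "new patients enrolled will be administered BXCL701 at the starting dose of 0.2 mg orally twice a day for the first 7 days", with escalation to 0.3 mg twice a day if tolerated.

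Section 7 also sends toxicity/efficacy summaries to the IND Office once 9, and then 17, patients per cohort have completed 9 weeks. Section 5.3.2 sends all SAEs to the IND Office, whatever the cycle or attribution.

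**The concern.** The trigger reuses an event built for the lead-in decision. In the lead-in, patients took 0.3 mg twice a day from Day 1, so a Cycle 1 window covered a full 14-day course at that dose. Under the step-up, the first full 14-day course at 0.3 mg twice a day comes in Cycle 2, after the window has closed. The protocol also expects immune-related toxicity at any time.

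Applied exactly as written, a treatment-related Grade 4 event or death first occurring in Cycle 2 or 3 adds nothing to the DLT rate. If the combination's serious toxicity were mainly delayed, the trigger could stay silent while a cohort with at least one response in its first 9 patients went on to 17. The 9-week report would show the events, but the plan does not say what number of them should lead to what action.

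**Working it through.** **The plan's own figures.** Section 7 gives no operating characteristics for the toxicity trigger, so there is none to reproduce. Its only computed design figures are for efficacy. Exact two-stage binomial calculation (stop at 0 of 9, promising at 3 or more of 17) gives 0.0466 / 0.4559 / 0.8122 at response rates 0.05 / 0.15 / 0.25, against the stated 0.046 / 0.455 / 0.813. These agree closely and do not bear on this point.

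**Exposure inside the window.** BXCL701 is taken on Days 1–14 of each 21-day cycle (Section 3), and 9 weeks is 3 cycles (Section 7).
- Step-up patient, escalated on Day 8, no holds: days at 0.3 mg twice a day are 7 + 14 + 14 = 35, of which 7 are in Cycle 1 (7/35 = 20%).
- Patient starting at 0.3 mg twice a day: 14 of 42 days (33%).

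**Count needed to fire at 9 patients.** 3/9 = 33.3%, which exceeds 33%. If 33% is shorthand for one third, 4/9 is needed. Section 7 states neither the look schedule nor whether cohorts are pooled. I take one look at 9 patients in one cohort, matching the first report. I do not use the 17-patient report, because by then that cohort's planned enrolment is complete.

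**Illustration (assumed rates).** 40% of patients have a DLT-type event by week 9, and one third of these (0.40/3 = 13.3%) have it in Cycle 1. With X binomial on 9 patients, P(X ≥ 3) = 1 − P(0) − P(1) − P(2).
- Cycle 1 only, p = 0.133: 1 − 0.276 − 0.382 − 0.235 = 0.107.
- Through week 9, p = 0.40: 1 − 0.010 − 0.060 − 0.161 = 0.768 (from unrounded terms).
- If 4 of 9 are needed, subtract P(3): 0.107 − 0.084 = 0.023, against 0.768 − 0.251 = 0.517.
- If half the events fall in Cycle 1 (p = 0.20), the Cycle 1 figure for at least 3 of 9 is 0.262.

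**Range.** Hold the Cycle 1 rate at an assumed 10% and let the later rate run over 10% / 20% / 30% / 40% / 50%. The current rule fires at 9 patients with probability 0.053 throughout, because later events do not enter it. Counting through week 9, p = 1 − 0.90 × (1 − later rate), and the probability is 0.236 / 0.483 / 0.708 / 0.864 / 0.950.

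**False pauses.** Assume a constant 5% risk per cycle. The three-cycle risk is 1 − 0.95³ = 0.143 and the six-cycle risk is 1 − 0.95⁶ = 0.265. P(at least 3 of 9) is 0.008 for Cycle 1 only, 0.125 over three cycles and 0.44 over six.

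**The case against.** A reader might infer that toxicity from Cycle 2 onward can never halt accrual. The documents do not support that. The 9-week summaries span three cycles and go to the IND Office for review. All SAEs go there too, unexpected related life-threatening or fatal ones within 24 hours, and SAEs also go to the IRB and FDA (Section 5.3.2). Nothing confines those reviewers to the 33% rule. What remains is that none of these routes carries a threshold or a stated accrual action. The explicit IND Office approval step covers only the move out of the lead-in, and the toxicity rules in Sections 6.2, 6.5 and 8.5.1 concern individual patients.

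A Cycle 1 window also has a rationale. Section 3.1 places the known hypotension risk mainly in the first week, and Section 6.5 says that immune-related events may occur at any time, not that they are mainly late. This supports keeping the Cycle 1 rule, but it does not cover immune-mediated events after it.

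The best objection concerns the remedy. Replacing the DLT with related events in any cycle would drop Cycle 1 events that now count whatever their attribution. An open-ended count would mix patients with unequal follow-up, and a 33% limit applied to a 21-day event is not calibrated for a longer one, as the rise to 0.44 over six cycles shows. These objections stand, and they limit the fix to an added, fixed-window count.

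**Conclusion.** The gap is real but bounded. The only written toxicity criterion for accrual in the Efficacy Stage is blind to events that first occur after Cycle 1; such events are reviewed, but with no threshold or accrual action. No stated figure in the plan is wrong because of this.

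Under the assumed 40% week-9 rate with one third of events in Cycle 1, the trigger fires at 9 patients with probability 0.11 rather than 0.77 (0.02 rather than 0.52 if 4 of 9 are needed). These sizes rest on assumed rates, an assumed look at 9 patients in one cohort, and every later event being counted; events judged unrelated would lower the larger figures. That the current rule does not respond to late toxicity follows from the definitions alone.

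The change is worth making. It is not evidence that the trial lacks safety oversight.

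**What to change.** In Section 7:

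1. Keep the Cycle 1 DLT rule unchanged, including that it counts events regardless of attribution.
2. Add that the 9-week toxicity report also counts patients with a DLT-type event from the Section 3 list, or a death, in Cycles 2–3 that is assessed as possibly related or related under Section 5.3.1. Add these patients to those with a Cycle 1 DLT, each patient counted once, over a fixed 9-week window.
3. Attach the existing suspend-and-discuss action to this cumulative count. The sponsor should confirm or set the threshold for the longer window, say whether 3 of 9 meets it, and state its false-pause probability under stated assumptions (for example 0.125 for at least 3 of 9 at 5% per cycle, against 0.008 for Cycle 1 only).
4. Reconcile the denominator. The condition in Section 3 for a patient "to be eligible for DLT assessment" cites 42 planned Cycle 1 doses, while twice-daily dosing on Days 1–14 gives 2 × 14 = 28.

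The cost is a few sentences in Section 7; the IND Office already receives the 9-week report and the SAEs. Pauses for discussion become more likely, and later events depend on investigator attribution. No dose or patient-level rule changes.

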7.1 Safety Analyses

All patients in the safety population will be included in the final summaries and listings of safety data for the lead-in patients. Summaries of AEs and other safety parameters will be provided as appropriate. Emphasis in the analysis of AEs will be placed on those that are treatment-emergent through 30 days after last dose of BXCL701 with pembrolizumab

Frequencies of patients experiencing at least 1 AE will be displayed by body system and preferred term according to Medical Dictionary for Regulatory Activities (MedDRA) terminology. Detailed information collected for each AE will include: a description of the event, duration, whether the AE was serious, nature of the event (single episode versus multiple episode), intensity (i.e., NCI CTCAE version 5 grade), relationship to study drug, action taken, clinical outcome, and whether the AE resulted in surgery or alternate procedures. Intensity (severity) of the AEs will be graded according the NCI CTCAE. The latest version of MedDRA and NCI CTCAE will be used.

Summary tables will be prepared to show the number of patients reporting AEs, the frequency of patient reports, and corresponding percentages. Percentages will be calculated using the number of patients in the safety population as the denominator. Within each table, the AEs will be categorized by MedDRA body system and preferred term. Additional subcategories will be based on event intensity and relationship to study drug. AE data will be presented across all cycles and for each cycle. The denominator for each cycle is those patients available at the start of the cycle who received a dose of BXCL701 for that cycle.

To the extent possible, AE relationship to either BXCL701 or pembrolizumab will be identified.

Individual patient listings will be prepared for all AE data.

Vital signs and ECOG performance status will be summarized by visits/cycles, using descriptive statistics applicable to continuous or categorical measures of these additional safety data. Summaries for the Lead-in and Efficacy Stages will be presented.

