7.2 Clinical Laboratory Analyses

All clinical laboratory values will be listed individually and tabulated in a manner to identify safety concerns on a per-patient basis. Listing tables will be prepared for each laboratory measure and will be structured to permit review of the patient data as they progress on treatment. The tables will list the cycle of treatment, BXCL701 dose for Lead-in data, and the associated NCI CTCAE grade. Descriptive summary statistics will be generated per laboratory parameter.

Summary tables will be prepared to examine the distribution of these toxicities per cycle.

Graphic displays and shift tables may be provided to illustrate results over time on study. Assessment of cumulative toxicities may be made.

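### Section 7 was not updated for the version 7 step-up: no safety output is planned by starting schedule or by BXCL701 dose at onset

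*Combined protocol and SAP*

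**What the plan says.** Section 3.1 gives the reason for the change: "The intent of step-up dosing is to immediately address a potentially serious side effect of hypotension", seen mainly in the first week among patients who start at 0.3 mg twice a day. It states that "the dosing schedule in the Efficacy Stage will be modified to implement a step-up dosing schedule during Cycle 1" and that, from version 7, "new patients enrolled will be administered BXCL701 at the starting dose of 0.2 mg orally twice a day for the first 7 days". Escalation to 0.3 mg twice a day then depends on tolerance. Section 3 starts Lead-in patients at 0.3 mg twice a day from Day 1. The schedule is thus set by the protocol version at enrolment, not by stage.

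Section 3 adds: "Patients enrolled to the Lead-in Stage will be also evaluated in the efficacy stage". On toxicity it says: "A DLT is defined as any of the following AEs occurring during Cycle 1". For the Efficacy Stage, Section 7 suspends accrual if the observed DLT rate exceeds 33%, without distinguishing schedules.

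Section 7.1 plans AE tables across all cycles and per cycle, with subcategories for grade and relationship, plus patient listings. After the vital signs and ECOG sentence it says: "Summaries for the Lead-in and Efficacy Stages will be presented". Section 7.2 says of the laboratory listings: "The tables will list the cycle of treatment, BXCL701 dose for Lead-in data, and the associated NCI CTCAE grade". Section 7 mentions neither the step-up nor hypotension.

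**The concern.** The schedule was changed during the trial for one named safety reason, yet the analysis section still reads as if every patient followed one schedule. Followed as written, the safety report need not separate patients by how they started, or events by the dose being taken. Two things are at stake. A fall in first-week hypotension could not be told apart from a shift to the second week, when the dose rises. And Cycle 1 DLT rates could be read as one quantity although they come from different exposures. Neither affects the response boundaries. Both affect how far the report describes the safety of either schedule, and overall safety and tolerability is a secondary objective.

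**Working it through.** **1. The plan's own figures.** No figure in the plan bears directly on this point. The design figures were reproduced to confirm that they are unaffected. With a stop at 0/9 and success at 3 or more of 17, Pr(success) = sum over x = 1 to 9 of Bin(x; 9, p) × Pr[Bin(8, p) ≥ 3 − x]. At p = 0.25 this gives 0.812 (stated 0.813), and the average size is 9 + 8 × (1 − 0.75^9) = 16.4 (stated 16.4). At p = 0.05 it gives 0.0466 (stated 0.046). Safety reporting by schedule changes none of these.

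**2. Stage against schedule** (Sections 3, 3.1 and 7).

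| Group | BXCL701 start |
|---|---|
| Lead-in, initial six | 0.3 mg twice a day from Day 1 |
| Efficacy Stage, enrolled before version 7 (number not given, possibly none) | 0.3 mg twice a day from Day 1 |
| Efficacy Stage, enrolled from version 7 | 0.2 mg twice a day for 7 days, then 0.3 mg twice a day if tolerated |

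Stage separates the schedules only if the middle row is empty and Lead-in patients stay out of the Efficacy Stage safety tables. The documents confirm neither condition.

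**3. Planned Cycle 1 dose.** Twice a day on Days 1 to 14 is 14 × 2 = 28 doses.

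- Flat: 28 × 0.3 = 8.4 mg, with 14 days at 0.3 mg twice a day.
- Step-up, escalated on Day 8: 14 × 0.2 + 14 × 0.3 = 2.8 + 4.2 = 7.0 mg, with 7 days at 0.3 mg twice a day. The reduction is 1.4 / 8.4 = 16.7%.
- Step-up, never escalated: 28 × 0.2 = 5.6 mg. The reduction is 2.8 / 8.4 = 33.3%.

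The first 14-day course at 0.3 mg twice a day for a step-up patient is therefore Cycle 2, outside the DLT window. One input needs reconciling: the DLT-evaluability text in Section 3 counts 42 planned doses in Cycle 1, against the 28 used here.

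**4. What the planned outputs show about week 1 and week 2.**

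- The Cycle 1 AE table merges Days 1–7 (0.2 mg twice a day) with Days 8–14 (0.3 mg twice a day). This holds whatever the enrolment mix.
- The AE fields named in Section 7.1 include duration, grade, relationship and action taken. Onset date and dose at onset are not named.
- Appendix A schedules Cycle 1 vital signs on Days 1, 2, 5, 8 and 15. Nominally none falls on Days 9–14, though the ±2-day windows on Days 8 and 15 can move a visit there.
- Appendix A also has blood pressure taken before each dose on Days 1–14, but Section 7 specifies no analysis of it.

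**5. The DLT rate.** An invented example shows what pooling can do. With 1 DLT in 12 flat-schedule patients and 4 in 8 step-up patients, the pooled rate is 5/20 = 25%, below 33%, while the step-up rate is 50%. The real counts are not in the documents.

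**6. What a split could support.** Assume the 34 evaluable patients divide evenly, 17 per schedule. With 0/17 events the exact upper 95% limit is 1 − 0.025^(1/17) = 19.5%. With 5/17 the exact interval is 10% to 56%. These intervals overlap, so even that contrast would be description, not proof.

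**The case against.** The plan gives more than a stage split. AE tables are also by cycle, grade and relationship, every AE is listed by patient, vital signs are summarised by visit, and blood pressure is taken before each dose. Schedule follows from the protocol version at enrolment, so a breakdown could be built afterwards. Per-cycle tables cover the step-up patients' first full course in Cycle 2, and the Lead-in assesses 0.3 mg twice a day from Day 1. The stage sentence follows one on vital signs and ECOG, so its reach to AE tables is an inference. The dose restriction in Section 7.2 concerns laboratory listings only. Comparing schedules is not an objective, and the numbers are too small for a test.

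All of this stands, and it rules out several stronger readings. A reader might infer that the AE tables are split by stage alone; Section 7.1 contradicts that. A reader might infer that the trial is unable to reveal anything about the step-up. The listings and blood pressure records allow a post hoc description, provided onset date and dose are captured. A reader might also take the opening sentence of Section 7.1 as placing every patient in the Lead-in summaries, but it can equally mean all Lead-in patients in the safety population. Likewise, evaluating Lead-in patients in the efficacy stage may refer to response only.

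These points do not answer the merged Cycle 1 row, the lack of any output by schedule, or the laboratory dose column confined to the stage where dose was fixed unless de-escalated. Small numbers argue against testing, not against showing the counts.

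**Conclusion.** The point holds as a gap in prespecification. Section 7 plans no safety output by starting schedule or dose at onset, so the version 7 change can be assessed only post hoc. The merging of two dose weeks in the step-up patients' Cycle 1 table is certain on the current text. The mixing of schedules in the Efficacy Stage AE tables and DLT rate is conditional: it needs either pre-version-7 Efficacy Stage enrolment or pooling with Lead-in patients. A reader might treat it as established, but the documents give no enrolment counts by version.

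Where schedules are compared or pooled, the planned Cycle 1 exposures differ by 17% (8.4 mg against 7.0 mg), assuming 28 doses and escalation on Day 8. The gap rises to 33% for a patient who never escalates. A reader might also expect added tables to show that step-up reduced hypotension. They would not: the groups are sequential, non-randomised and drawn from at most 42 recruited patients. This is a modest, inexpensive reporting improvement that leaves the response boundaries and the suspension rule as they are.

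**What to change.** - In Section 7.1, add descriptive summaries with exact intervals of hypotension, dizziness, edema, hypovolemia, dose holds and DLTs, by starting schedule (enrolled before or from version 7), for Cycle 1 Days 1–7, Cycle 1 Days 8–21 and Cycle 2.
- In Sections 7.1 and 7.2, show AE onset date and BXCL701 dose in the AE and laboratory listings for both stages.
- Report the DLT rate by starting schedule beside the pooled rate, leaving the suspension rule unchanged. State whether Lead-in patients enter that rate and the Efficacy Stage AE tables.
- Reconcile the dose count in the DLT-evaluability text with the Days 1–14 twice-daily schedule. Also reconcile Section 6.1, which gives the 0.2 mg start without a duration, with the 7 days in Sections 3 and 3.1.

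The cost is a few extra tables and, if not already captured, two AE fields. Cells will be small, so the tables should be labelled descriptive, with no test between schedules.
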